Appendix I: Neurocognitive testing for dedicated centers – Side study

The assessment of neurocognitive testing as specified in this appendix relates to a side study to the main protocol. This study will be performed at a number of dedicated centers, on a voluntary basis. Institutions with patients participating in the quality of life/neurocognitive function components of this study must meet certification requirements for administering neurocognitive assessments. See Appendix II for details.

1. Schedule and tests performed

Comprehensive neurocognitive testing will be performed at randomization and at every year from randomization up to tumor progression or death.

The tests that constitute the neurocognitive function battery were selected because they are widely used standardized psychometric instruments that have been shown to be sensitive to the neurotoxic effects of cancer treatment in other clinical trials. Neurocognitive function has also been demonstrated to predict tumor progression and independently predict survival for patients with CNS tumors. This battery has furthermore been demonstrated to be practical in terms of cost and burden to the patient, with good compliance in multicenter trials. They are widely used, standardized psychometric instruments with published normative data that take into account age and, where appropriate, education, gender and handedness. The tests were also selected to minimize the effects of repeated administration. These tests are to be administered by a certified examiner and require 25 minutes or less to complete.

To reduce practice effects, parallel versions of the tests will be developed and will be made available to all participating centers.

Self-reported cognitive function will be assessed with a six-item scale developed for use in the Medical Outcomes Study (MOS scale). This scale assesses day-to-day problems with cognitive function, such as difficulty with reasoning and problem solving, slowed reaction time, forgetfulness, and problems with concentration.

2. Neurocognitive Function Testing Certification

The healthcare professional (e.g., nurse, psychologist) who is responsible for test administration in this study requires pre-certification by [name] in order to participate in this protocol. For the exact procedure see appendix II.

In short, test and data recording forms are available on a password-protected website:

www.vumc.nl/neurooncology

Test instructions and administration procedures will be provided upon agreement to participate in the side-study. A training video of test administration and data collection procedures are accessible through a password-protected website at M. D. Anderson Cancer Center for review and reference during this study. This video must be reviewed with the test Instructions for the Neurocognitive Function Battery by anyone who will administer neuropsychological assessments. The post test associated with this video must be completed and faxed to [name]. Passwords for the website will be provided by [name], for which he can be contacted by e-mail (see below).

3. Statistical analysis

Overall power calculation for estimating sample size requirements were based on the following criteria: (1) 4 treatment arms, (2) a minimal effect size $f(V)$ of 0.25, (3) power $(1-\beta)$ of 0.95, and (4) 3

neurocognitive follow-up assessments after randomization. With $\alpha = 0.05$, 129 patients in total ($n=32$ per treatment arm) are needed to perform repeated measures MANOVA, with potential within and between groups interactions. With a minimal effect size $f(V)$ of 0.15 353 patients in total ($n=88$ per treatment arm) are needed. Considering that not all centers will participate in the neurocognitive side-study, the present study meets these sample size requirements.

We will use various models, including the Cox proportional hazards model and mixed and hierarchical linear models. Alternatively, we can use multilevel modeling to detect differences between the four groups over time. These repeated measure analyses can also be supplemented with a psychometric analysis of changes in test performance using the Reliable Change (RC) Index [10]. The difference between the pre-treatment baseline and follow-up assessments will be evaluated by the RC index. This index is derived from the standard error of measurement (SEM) for each test in the battery. The SEM is calculated from the test-retest reliability (r) and the standard deviation of test scores (SD): $SEM=SD(1-r)^{1/2}$. The standard error of difference is then calculated: $SE\ diff=[2(SEM^2)]^{1/2}$. A reliable change (RC) in test scores from baseline to follow-up is considered significant if it is within $\pm (1.64)(SE\ diff)$, a 90% confidence interval. For each subject, the difference between the pre-treatment baseline and each follow-up assessment will be coded (according to the RC index) as 1 (deterioration), 2 (no change), and 3 (improved). Frequency tables will show the percentage of patients in each treatment protocol who show meaningful losses or gains in the various test domains over the course of the study. Treatment group differences can be compared using chi-square analysis and Cochran's and Mantel-Haenszel statistics.

4. Data Management

All tests will be identified by the date of assessment and EORTC patient identification number (seqid). The test results from all participating centers and groups will be sent to the EORTC Headquarters together with the regular patient documentation. The EORTC Headquarters will then transfer the forms relating to the neurocognitive assessment side study to the Coordinator of the Side Study ([name], VU University Medical Center, Amsterdam, The Netherlands).

The information related to the side study will be entered in a specific database in Amsterdam. Care will be taken that the patient identification is recorded.

At the end of the clinical trial after publication of the main trial results, the information from the clinical database that is needed for the analysis of the side study data will be transferred to the Coordinator of the Side Study, after completion and approval of the Request for External Release of Data as specified in EORTC Policy number 8.

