8.2.3.4 Analysis of MMSE

The distribution of the MMSE at each time point of evaluation (see chapter 6) will be described on the four treatment arms separately using means and their associated standard error (a longitudinal plot will be considered). Median and range will also be computed.

Box-plots will be used to represent MMSE score distribution at baseline and at key time-points of evaluation (e.g. Baseline, 4 weeks of radiotherapy, at every 3 monthly visit where form compliance is sufficient). The proportion of patients with 'normal' and 'impaired' MMSE score will also be displayed.

Similarly to Brown et al. the changes in MMSE scores over time will be summarized in the four treatment groups by the proportion of patients with significant increase (> plus 3 points), stable (- 3 points to + 3 points) or significant decrease (> minus 3 points) of the MMSE score at the key time points of evaluation. For both questions (I and II), the distributions will be compared at each evaluation point using a Chi-square test for trend. A Bonferroni adjustment of the type I error rate will be used to correct for multiple testing.

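### The neurocognitive side study compares four arms with no contrast for the concurrent or the adjuvant question, no deciding score and no multiplicity rule

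*Combined protocol and SAP*

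**What the plan says.** Appendix I, section 3 sizes the side study for four arms and three follow-up assessments at 95% power. It states that 129 patients (effect size 0.25) or 353 patients (0.15) "are needed to perform repeated measures MANOVA, with potential within and between groups interactions". The only significance level, 0.05, stands in that sizing sentence.

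The analysis text then says: "We will use various models, including the Cox proportional hazards model and mixed and hierarchical linear models". It continues: "Alternatively, we can use multilevel modeling to detect differences between the four groups over time". Reliable Change coding of each follow-up against baseline may supplement these analyses, and "Treatment group differences can be compared using chi-square analysis and Cochran's and Mantel-Haenszel statistics".

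The section names no score, visit or contrast as deciding, sets no multiplicity rule, and does not mention Questions I and II.

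Elsewhere the plan follows the factorial design. Section 8.1.1 defines the two questions, and 8.2.3.2 fits the survival models with an indicator for each. For the MMSE, section 8.2.3.4 says: "For both questions (I and II), the distributions will be compared at each evaluation point using a Chi-square test for trend", with a Bonferroni adjustment. Section 2.2 lists late effects on cognition among the secondary objectives.

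**The concern.** The trial randomises two components and asks about each. A four-arm test asks only whether the arms differ somewhere. If it is positive, the reader still does not know whether concurrent or adjuvant temozolomide is responsible, which is what a clinician weighing late toxicity needs to know. It also spends degrees of freedom on differences that neither question asks about.

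The battery yields several scores, each assessed yearly. Without a deciding score or an adjustment, one nominally significant difference among many could be read as a cognitive effect. Section 4 of the appendix transfers the clinical data for this analysis only after the main results are published, so any choice left open would be made with those results known.

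**Working it through.** **1. The plan's own sample size.** Inputs from Appendix I, section 3: k = 4 arms, three follow-ups plus baseline (p = 3 changes over time), alpha 0.05, f(V) = 0.25 or 0.15. For the arm-by-time test (Pillai's trace):

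- s = min(p, k − 1) = 3 and df1 = 3 × 3 = 9.
- df2 = s(N − k − p + s) and λ = N·s·f(V)².
- N = 129: df2 = 3 × 125 = 375, λ = 129 × 3 × 0.0625 = 24.19, power 95.1%.
- N = 353: df2 = 1047, λ = 353 × 3 × 0.0225 = 23.83, power 95.0%.

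Both stated sizes reproduce exactly. They cover one omnibus 9-df test on one score.

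**2. Four-arm test against factorial contrast at one visit.** Assume one component shifts the mean by d standard deviations and the other has no effect. Then λ = N·d²/4 for both tests.

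| | λ | 3 df, 5% | 1 df, 5% | 1 df, 2.5% |
|---|---|---|---|---|
| N = 128, d = 0.5 | 128 × 0.25/4 = 8.00 | 64% | 80% | 71% |
| N = 352, d = 0.3 | 352 × 0.09/4 = 7.92 | 64% | 80% | 71% |

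**3. The same comparison over time, N = 129.** Hold the omnibus effect at the plan's value: V = 3 × 0.0625/1.0625 = 0.1765. A question-by-time contrast has 3 and N − 6 = 123 df, with λ = N·V/(1 − V) for the share of V that it carries.

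- Whole effect in one question: λ = 129 × 0.2143 = 27.6. Power is 99.1% at 2.5%, against 95.1% for the omnibus test at 5%.
- Effect split equally: V = 0.0882 each, λ = 129 × 0.0968 = 12.5. Power is 76.5% per question at 2.5%.

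Full adjustment over seven scores by two questions uses 0.05/14 = 0.00357 at the first step. Power per score is then 95.2% (one question) or 51.6% (split). The omnibus test adjusted over seven scores (0.05/7) has 82.3%.

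**4. Multiplicity.** Counting from Appendices I to III, there are three HVLT-R scores (free recall, delayed recall, delayed recognition), Trail Making A and B, COWA and the MOS scale: about seven. The documents give no correlations, so a range is shown, with no true effect and 5% per test.

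- One test per score, independent: 1 − 0.95⁷ = 30.2%.
- One arm-by-time test per score, simulated with 128 patients: 29% at between-score correlation 0, and 22% at 0.6.
- One single-visit four-arm test per score, simulated: 30% at correlation 0, 23% at 0.5 and 19% at 0.7.
- Reliable Change chi-square tests for seven scores at three visits (21 tests, assumed correlation 0.7 over time): about 53–56%. Counting these or the arm-by-time tests: about 61–67%.

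**The case against.** Several points on the other side stand.

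- The side study is voluntary and limited to dedicated centers. The summary table in section 6.6 marks the cognitive exam as optional translational research, and nothing presents it as confirmatory.
- The MMSE is the cognitive measure in the main analysis plan, and it is tested by question with adjustment. Objective 2.2 therefore does not rest on this battery alone.
- Mixed, hierarchical and multilevel models are largely one class, and Reliable Change is described as a supplement. A reader might infer a menu of interchangeable analyses with no order among them. The text does not support that.
- A reader might also infer that a false cognitive finding is likely. One longitudinal test per score gives about 20–30%. The figure passes 50% mainly when per-visit Reliable Change comparisons, which the text only permits, are all counted. Counting just the four tests tabulated in Appendix II gives 1 − 0.95⁴ = 18.5%. The 5% level itself comes from the sizing sentence.
- The gain in power is not general. It holds for an effect of one component. If the effect is split, each question contrast has less power than the omnibus test.
- A four-arm comparison can show an interaction, which two main-effect contrasts would hide.

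None of this supplies a contrast that answers Question I or II, a deciding score, or an adjustment. Section 7.3 refers the reader to Appendix I for the battery, and section 8.2 does not cover it.

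**Conclusion.** The concern holds in a limited form. As written, the side study tests whether four arms differ and cannot attribute a difference to concurrent or adjuvant temozolomide. For an effect of one component, the factorial contrast does better even at 2.5%: 71% against 64% at one visit, and 99% against 95% over time. For an evenly split effect it has 76.5% per question, but it answers the question asked. The unadjusted risk of at least one false positive is about 20–30% with one test per score. It is higher if the optional per-visit comparisons are also tested.

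These figures assume equal arms, complete data to the third yearly assessment, about seven scores, and correlations that the documents do not give. The point is worth fixing because the remedy is cheap. It does not touch the survival or MMSE tests.

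**What to change.** In Appendix I, section 3:

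- State that the mixed (multilevel) repeated-measures model includes indicators for Questions I and II, and that these two contrasts over time are the main side-study comparisons.
- Adjust by Bonferroni or Holm across questions and scores, in line with section 8.2.3.4, and list the scores that count.
- Keep the four-arm comparison with its interaction, the Cox models and the Reliable Change tables as supplementary and exploratory.
- A composite score is optional. If one is used, reverse the sign of the Trail Making times, where higher is worse, so that harm does not cancel against the other scores. State whether the MOS scale is included.

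This should be settled before the clinical data are transferred for the side-study analysis. It needs wording only, with no new patients or assessments. The cost is less power for any single score after adjustment: at the first Holm step, about 95% if the effect lies in one question, and about 52% per question if it is split.

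### Appendix I calls a change in test score significant when it lies inside the measurement-error range, which is the no-change range

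*Combined protocol and SAP*

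**What the plan says.** Appendix I describes neurocognitive testing as a side study: "This study will be performed at a number of dedicated centers, on a voluntary basis". Its section 3 first lists the main models for the test scores and then adds an individual-level analysis: "These repeated measure analyses can also be supplemented with a psychometric analysis of changes in test performance using the Reliable Change (RC) Index".

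The index is built in three steps. The standard error of measurement (SEM) comes from the test's standard deviation and its test-retest reliability. The standard error of the difference between two assessments (SEdiff) comes from the SEM. The decision rule follows: "A reliable change (RC) in test scores from baseline to follow-up is considered significant if it is within" plus or minus 1.64 SEdiff, which the text labels a 90% confidence interval.

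The next sentence says that each patient's difference from baseline "will be coded (according to the RC index) as 1 (deterioration), 2 (no change), and 3 (improved"). Frequency tables by treatment are then to show the percentage of patients with "meaningful losses or gains in the various test domains over the course of the study". Chi-square, Cochran and Mantel-Haenszel statistics are named for comparing the groups.

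**The concern.** SEdiff as defined here contains measurement error and nothing else. The range of plus or minus 1.64 SEdiff around zero is therefore where differences are expected to fall when the patient has not changed. A rule meant to detect reliable change has to flag differences beyond that range; this one flags those inside it.

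It is the only rule in the available text that turns a score difference into code 1, 2 or 3. An analyst who programs it as written would label the most stable patients as changed and those with the largest losses or gains as not changed. The side study looks for late cognitive effects of treatment, so its frequency tables would then point the wrong way on the very thing they are meant to show.

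**Working it through.** **Inputs, all from Appendix I, section 3**

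- SEM = SD × (1 − r)^½
- SEdiff = (2 × SEM²)^½
- Cut-off: ±1.64 SEdiff, labelled 90%
- Codes: 1 deterioration, 2 no change, 3 improved

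**Step 1: reproduce the plan's own figure.** For a standard normal variable, Φ(1.64) − Φ(−1.64) = 0.8990. The exact multiplier for 90% is 1.645. The formulas, the 1.64 and the 90% label agree to rounding, so only the direction of the rule is in question.

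**Step 2: what the range means.** With no true change, the observed difference divided by SEdiff has mean 0 and standard deviation 1. It falls inside ±1.64 with probability 0.899 and outside with probability 0.101, about 0.0505 on each side.

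**Step 3: compare with the codes.** A range centred on zero has one inner region and two outer ones. Three codes, with one for no change and two for change in opposite directions, match it only if 'no change' is inside and the other two codes are outside. The literal rule allows no such match: small differences count as significant, while large losses and large gains share the remaining category.

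**Step 4: size of the reversal.** Let the true shift be μ in SEdiff units and the observed change be normal with mean μ and standard deviation 1.

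- Flagged as written = Φ(1.64 − μ) − Φ(−1.64 − μ)
- Flagged under 'outside' = 1 − that value

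| True shift μ (SEdiff) | Flagged as written | Flagged under 'outside' |
|---|---|---|
| 0 | 89.9% | 10.1% |
| 1 | 73.5% | 26.5% |
| 1.5 | 55.5% | 44.5% |
| 1.64 | 49.95% | 50.05% |
| 2 | 35.9% | 64.1% |
| 3 | 8.7% | 91.3% |

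As written, the flagged share falls as the true change grows. The two readings agree only near a shift of 1.64 SEdiff.

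**Step 5: dependence on SD and r.** The section states neither value. In SEdiff units the table needs neither. In raw-score terms the cut-off does depend on both: for an assumed r of 0.6, 0.7, 0.8 and 0.9, 1.64 SEdiff equals 1.467, 1.270, 1.037 and 0.733 SD.

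**The case against.** The strongest reply is that nobody would apply the rule literally. The index is named and cited, and the three-code scheme in the next sentence makes sense only under the usual reading. On that view this is a one-word editorial slip, and the table above describes something unlikely to happen. Most of this stands, and it is why the point is minor. It does not make the sentence right: a prespecified classification rule should not need its reader to reverse it.

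A second reply concerns the group comparisons. If patients are only split into flagged and not flagged, swapping the labels leaves the Pearson chi-square and its p-value unchanged. That is correct. What reverses is the direction: the arm with more real change appears to have less. With all three codes the literal rule would also merge large losses with large gains, but the effect of that on the test statistic was not computed and is not claimed.

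Third, the percentages assume no practice effect. Section 1 of Appendix I promises parallel versions of the tests, while Appendix II gives alternate forms for only two of them (HVLT-R and COWA). Practice effects on the Trail Making Test are therefore plausible, and the figures are illustrative. The reversal itself does not depend on them.

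Fourth, the appendix cites a source numbered [10] for the index, and the list behind that number is not in the text available here. The statement that no other rule exists is limited to the visible text.

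**Conclusion.** The rule is wrong as written. The construction of SEdiff, the 90% label, the three codes and the purpose of the tables all require a significant change to lie outside ±1.64 SEdiff. Followed literally, the rule flags 89.9% instead of 10.1% of unchanged patients and 8.7% instead of 91.3% of those shifted by 3 SEdiff. These figures rest on normal measurement error and no practice effect, and they count flagged against not flagged without a split by direction.

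The reach is small. The codes supplement other analyses of a voluntary side study. The text introduces them as something that can be added but then says the coding will be done, so their optional status is not fully clear. Overall survival, progression-free survival, MMSE, safety, the side study's longitudinal models and its sample size, which is based on repeated-measures MANOVA, do not use them. Severity: minor.

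**What to change.** In Appendix I, section 3, replace 'within' with 'outside' and add the mapping: code 1 for a change of more than 1.64 SEdiff for the worse, code 3 for a change of more than 1.64 SEdiff for the better, and code 2 for a change within ±1.64 SEdiff.

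Define worse and better separately for each test rather than by the sign of the difference. Trail Making is scored as time to completion, so a higher value is worse; HVLT-R recall and COWA count correct responses, so a higher value is better.

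The change is one word plus one clarifying sentence, with no cost in data, patients or time. Under the data management section of Appendix I, the clinical data needed for this analysis go to the side-study coordinator only after the main results are published, so the rule can be corrected before that transfer. If the transfer has already taken place, the analysis program should be checked to confirm which direction was used.

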Appendix II

Certification and administration procedures for the neurocognitive test battery

General Procedures: Certification for Test Administration

The healthcare professional (e.g., nurse, psychologist) who is responsible for test administration in this study requires pre-certification by [name] in order to participate in this protocol.

- Test and data recording forms are available on the password-protected website provided by [name]. Test instructions and administration procedures are provided in Appendix III. The instructions must be reviewed along with the test forms and retained for reference.
- A training video of test administration and data collection procedures are accessible through a password-protected website at M. D. Anderson Cancer Center for review and reference during this study.
- This video must be reviewed with the “Test Instructions for the Neurocognitive Function Battery” found in Appendix III by anyone who will administer neuropsychological assessments.
- The post test associated with this video must be completed and faxed to [name].

To obtain website and password information for the training video, contact:

[name]
VU Medical Center
Amsterdam, The Netherlands
Tel: [name]
e-mail: [contact]

- Prior to the enrollment of any patient onto the study, the healthcare professional who will be evaluating patients must complete a “practice” assessment, including completion of test forms/score sheets, neurocognitive evaluation summary form, and complete and sign the Certification Worksheet (Appendix IV). Fax the practice tests, score sheets, neurocognitive evaluation summary form, training video post test, and signed Certification Worksheet to the attention of [name], [contact].
- If there are administration or procedural errors, [name] will discuss the test administration and scoring issues over the phone with the healthcare professional (5-10 minutes). If the health professional meets criteria for certification, notification of certification will be sent to both the site and to EORTC, and study enrollment may commence.
- The first case for each certified examiner should be faxed to [name]. Please send the test forms and all test summary and score sheets and include contact information (name, phone, email) for the certified examiner. [name] will review test forms and summary sheets for quality control purposes. Procedural deviations (if any) will be identified, and sites will be notified of the results of the review. If significant procedural variations are noted, re-training (‘re-certification’) of the test administrator will be requested.
- Completed test forms must be signed by the certified test administrator. [name] will be available by telephone and e-mail if questions arise about the testing procedures. [name] may be contacted at [contact] or email: [contact].
- Results of the HLVT-R, COWA, and Trail Making Tests should be recorded on the Neurocognitive Evaluation Summary Form (CS), and the original patient tests/forms will not be submitted to [name] (copies of test forms and summary sheets for the first case will be sent to [name] per Appendix II). All tests will be identified by the date of assessment and EORTC patient identification number (seqid). The test results will be sent to the EORTC Headquarters together with the regular patient documentation. The EORTC Headquarters will then transfer the forms relating to the neurocognitive

assessment side study to the Coordinator of the Side Study ([name], VU University Medical Center, Amsterdam, The Netherlands).

Summary of Requirements for Examiner Approval for EORTC 26053_22054

Prior to testing a patient, potential examiners must:

1. Read Appendix II and III
2. Obtain copies of the neurocognitive tests
3. Watch the training video available on a password-protected website. To obtain website and password information, contact [name]. ([contact]).
4. Complete the training video post test
5. Complete a “practice” assessment
6. Complete the Certification Worksheet (Appendix IV)
7. All materials (i.e., post test, complete practice assessment and scoring forms, certification worksheet) must be faxed to [name], who will score it and review any procedural errors with the trainee. If the trainee demonstrates competency, he/she will be notified of the approval to administer the tests to study subjects as part of EORTC 26053_22054. An approval notice will be sent to EORTC for their records and to ensure that only EORTC 26053_22054-approved examiners are testing subjects on protocol EORTC 26053_22054.
8. After certification, each examiner must fax to [name] all test forms and data summary sheets for their first case.

Neurocognitive Assessment

The tests that constitute the neurocognitive function (NCF) battery were selected because they are widely used standardized psychometric instruments that have been shown to be sensitive to the neurotoxic effects of cancer treatment in other clinical trials. NCF has been demonstrated to predict tumor progression and independently predict survival for patients with CNS tumors. This battery has also been demonstrated to be practical in terms of cost and burden to the patient, with good compliance in multicenter trials. They are widely used, standardized psychometric instruments with published normative data that take into account age and, where appropriate, education, gender and handedness. The tests were also selected to minimize the effects of repeated administration. These tests are to be administered by a certified examiner and require 25 minutes or less to complete.

Cognitive Domain	Test	Time to Administer (minutes)
Memory	Hopkins Verbal Learning Test–Revised	8
Visual-motor processing speed	Trail Making Test Part A	5
Executive Function	Trail Making Test Part B	7
Verbal fluency	Controlled Oral Word Association	5
		Total time: 25 minutes

Neurocognitive Assessment – Sequencing of Alternate Forms

Two of the tests to be administered have alternate forms or versions in order to reduce the effects of practice. See the table below for the versions to be administered at pre-entry and subsequent sessions. The forms should continue to be alternated in this order for the duration of the study. The forms packet will contain alternate versions of these neuropsychological tests.

TEST	Study Registration	1 month post RT/TMZ	3rd visit	4th visit	5th visit	6th visit	7th visit
HVLT-R	Form 1	Form 2	Form 3	Form 4	Form 5	Form 6	Form 1
COWA	'C-F-L'	'P-R-W'	'C-F-L'	'P-R-W'	'C-F-L'	'P-R-W'	'C-F-L'

Additional comments:

1. Testing should be completed in one session. Test instructions must be followed verbatim with every patient at every study visit. All tests should be completed in black pen.
2. Tests should be administered in the following order to every patient and at every study visit: HVLT-R Free Recall; Trail Making Test Part A; Trail Making Test Part B; COWA; HVLT-R Delayed Recall; and the HVLT-R Delayed Recognition.
3. You may fill the 20-minute delay interval between COWA and HVLT-R Delayed Recall with QOL questionnaires.
4. Follow the instructions on the Forms Packet Index before submission of forms to [name].
5. Please keep all original test records. In the event of questions, contact [name]. Copies of the test forms and summary sheets for the first case from each site must be reviewed by [name]. Additionally, test results are not submitted to [name]. All tests will be identified by the date of assessment and EORTC patient identification number (seqid). The test results will be sent to the EORTC Headquarters together with the regular patient documentation. The EORTC Headquarters will then transfer the forms relating to the neurocognitive assessment side study to the Coordinator of the Side Study ([name]).
6. All test results are recorded on the Neurocognitive Evaluation Summary Form (CS), which is found in the Forms Packet. Study/case specific labels must be applied to all forms.
7. Patients should not be given copies of their tests to avoid learning the material between test administrations.
8. Before dismissing the patient, thank the patient for his/her cooperation. Remind the patient of his/her next appointment and that these tests will be repeated.
9. In the event that a patient cannot complete a given test, please write the reason(s) on the test form AND the data summary form.

